6.3. Measures to Minimize Bias: Randomization and Blinding

6.3.1. Allocation to Study Intervention

The investigator will assign participant numbers to the participants as they are screened for the study. Pfizer will provide a randomization schedule to the investigator and in accordance with the randomization code, the participant will receive the study treatment regimen assigned to the corresponding randomization number.

Investigators and participants will remain blinded to each participant's assigned study intervention throughout the course of the study. In order to maintain this blind, an otherwise uninvolved third party (for example, pharmacist) will be responsible for the preparation and dispensing of all treatments, according to the randomization schedule and assigned treatment for the individual participant.

6.3.2. Breaking the Blind

The method for breaking the blind in this study will be manual. In case of an emergency, the investigator has the sole responsibility for determining if unblinding of a participant's treatment assignment is warranted. Participant safety must always be the first consideration in making such a determination. If the investigator decides that unblinding is warranted, the

investigator should make every effort to contact the Medical Monitor prior to unblinding a participant's treatment assignment unless this could delay further management of the participant. If a participants' treatment assignment is unblinded, the sponsor must be notified within 24 hours after breaking the blind. When the blinding code is broken, the reason must be fully documented and entered on the data collection tool (DCT).

CRU Pharmacy must ensure that any opened randomization information is secured appropriately again after consultation.

Blinding codes should be broken only under exceptional circumstances when knowledge of the actual treatment code is absolutely essential for further management of the participant. Investigators are encouraged to discuss with a member of the study team if they believe that unblinding is necessary.

Blood specimens will be obtained from all participants for PK analysis to maintain the study blind at the investigator site. Only the investigator site staff will be blinded to study treatments. A limited number of Pfizer study team personnel will be unblinded to participant treatments in order to permit real-time interpretation of the safety data and provide information necessary to determine dose and regimen of the optional cohort, if enrolled. The blinded study monitor, if assigned, will remain blinded to treatment until all monitoring for the study has been completed. Specimens from participants randomized to placebo will not be routinely analyzed. To minimize the potential for bias, treatment randomization information will be kept confidential by Pfizer unblinded personnel and will not be released to the blinded investigator or blinded investigator site personnel until the study database has been locked or the investigator requests unblinding for safety reasons.

6.4. Study Intervention Compliance

Investigational product will be applied under the supervision of investigator site personnel. The application site of each participant will be examined following dosing to ensure the investigational product was topically applied. The date and time of each dose administered will be recorded in the source documents.

6.5. Dose Modification

No dose modification is anticipated for Cohort 1 and Cohort 2 in this study. Dose and dosing regimen in Cohort 3 and Cohort 4 may be determined based on review of emerging data from Cohort 1 (for Cohort 3 only) and Cohort 1, Cohort 2 and Cohort 3 (for Cohort 4 only).

6.5.1. Dose Stopping Rules

No dose escalation is planned for this study.

The dosing will be terminated based on the following criteria:

• If 50% or more of the participants receiving active drug (but not participants receiving placebo) develop similar clinically significant laboratory, ECG, or vital sign abnormalities, in the same organ class, indicating dose-limiting intolerance.

- Severe nonserious AEs, considered as, at least, possibly related to study intervention administration, in 2 participants at a given dose level (but not participants receiving placebo), independent of within or not within the same system organ class, indicating dose-limiting intolerance.
- Dosing will be paused for any SAE that occurs in a participant receiving active treatment until causality is fully assessed by the PI and sponsor. Dosing may resume if the SAE is determined to be not drug-related by the PI and sponsor. If the SAE is determined to be either drug-related or unknown, either dosing will cease or the SAE will be evaluated by the sponsor's protocol review committee (or similar review group), which is independent of the study team and investigators. If the protocol review committee determines that dosing may resume, a plan that mitigates risks to participants with the resumption of dosing will be implemented. Such a plan could include a revision of inclusion/exclusion criteria, repeating or reducing the dose, or adding appropriate safety monitoring.
- Draize score will be incorporated in individual dose application decisions. The dose will not be considered well-tolerated and application of corresponding IP will be terminated if:
 - Persistent Draize scoring of ≥ 3 in more than 50% participants in each cohort.
 - Persistent Draize score of 4 in 2 or more participants in a cohort. In addition, the study will be paused for further assessment of any Draize score of 4.
 - Clinically significant skin abnormalities following application of the IP (based on the judgment of the medical provider/investigator) in 2 or more participants in a cohort. These include persistent moderate to severe skin findings at the site of active drug application: edema, papules, vesicles, bullae, weeping, fissuring, and erosions.
 - Within a participant, "Persistent" is defined as the presence of skin findings in at least 2 consecutive assessment periods at least 8 hours apart.
- Other findings that, at the discretion of the study team and investigator, indicate that dosing should be halted.

Optional cohort dosing will occur after review of all available safety data in a minimum of 4 participants (3 active: 1 vehicle) dosed in Cohort 1, Cohort 2 and Cohort 3 (for Cohort 4 only) up to 10 days post-dose.

6.5.2. Individual Stopping Rules

If an individual participant exceeds any of the following, the participant will be discontinued from the study and will enter early termination visit as per SoA:

- Any of the following values (to be confirmed at 24 hours $[\pm 8 \text{ hours window}]$):
 - ECG changes (as described in Section 7.1.1), potential acute kidney injury (as described in Section 7.1.2), and potential drug-induced liver injury (as described in Appendix 6);
 - Any laboratory values or clinically significant findings meeting criteria of CTCAE v5.0 Grade 3 or greater.
- Any SAE (irrespective of relatedness to study drug).
- Any adverse dermal findings that, at the discretion of the study team and investigator, indicate that dosing should be halted.
- Please refer to Section 7 for additional individual discontinuation criteria.

6.6. Continued Access to Study Intervention After the End of the Study

No intervention will be provided to study participants at the end of the study.

6.7. Treatment of Overdose

For this study, the maximum feasible formulation of IP specified below, Q12H to designated surface area within a 24-hour time period ± 2 hour will be considered an overdose:

- any dose of PF-07295324 greater than 0.12% within a 24-hour time period ±2 hours will be considered an overdose.
- any dose of PF-07259955 greater than 2% within a 24-hour time period ±2 hours will be considered an overdose.

There is no specific treatment for an overdose.

In the event of an overdose, the investigator should:

- 1. Contact the medical monitor within 24 hours.
- 2. Closely monitor the participant for any AEs/SAEs and laboratory abnormalities for at least 5 half-lives or 28 calendar days after the overdose of PF-07295324 and PF-07259955 (whichever is longer).
- 3. Document the quantity of the excess dose as well as the duration of the overdose in the CRF.

- 4. Overdose is reportable to Pfizer Safety only when associated with an SAE.
- 5. Obtain a blood sample for PK analysis within 1 day from the date of the last dose of study intervention if requested by the medical monitor (determined on a case-by-case basis).

Decisions regarding dose interruptions or modifications will be made by the investigator in consultation with the medical monitor based on the clinical evaluation of the participant.

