d. Margins have been calculated relative to PF-07259955 NOAEL unbound C_{avg} =1691 ng/mL in 6 week oral GLP toxicology study in rat; systemic safety margins have been calculated based on unbound plasma exposures.

As summarized in Table 4, following topical administration of maximal feasible formulation (2%) of PF-07259955, Q12H, on approximately 20% BSA, the projected average steady state unbound plasma concentration (C_{avg}) is approximately, 16 ng/mL (38.4 nM).

Based on the projected steady-state systemic exposure [16 ng/mL (38.4 nM) is \sim 3.7-fold below the unbound IFN γ IC₅₀ (143 nM)], following topical administration of PF-07259955 (2%, Q12H, 20%BSA).

This highest projected exposure is approximately 110-x below the rat unbound NOAEL C_{avg} of 1691 ng/mL. Similarly, minimal, non-adverse local irritation is anticipated at this maximum feasible formulation based on 6 week dermal toleration assessment in minipigs (Section 2.2.3.2). The NOAEL in the PF-07259955 pivotal 6-week dermal toxicity study in minipigs was 0.74 mg/cm²/day, resulting in an ~9.3x dose margin based on an anticipated clinical application rate of 2 mg/cm² and dose of 0.08 mg/cm²/day (2% cream, BID).

Overall, multiple topical administrations of PF-07259955 (2%), in healthy adult participants are expected to be safe and well tolerated, locally and systemically.

Beyond Cohort 1 and Cohort 2, up to 2 optional cohorts (Cohort 3 and potentially Cohort 4) of up to 6 healthy adult participants in each cohort may be enrolled in this study. The optional cohorts may be used to repeat the doses studied in previous cohorts, explore lower formulation strength, or repeat the 0.12% formulation strength on lower body surface area, or at less frequent dosing interval on approximately 20% BSA. All cumulative safety data from Cohort 1 and Cohort 2 will be used to determine the formulation strength, %BSA, and dosing regimen to be administered to participants enrolled in optional cohorts. The formulation strengths and frequency of dosing of PF-07295324 or PF-07259955 to be investigated in the optional Cohort 3 and/or Cohort 4 will not exceed that of Cohort 1 or Cohort 2.

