6.1. Study Intervention(s) Administered

For this study, the investigational products are PF-07295324 (0.12%), ointment and PF-07259955 (2%), cream, as well as the corresponding vehicles for each IP.

Both the IPs (PF-07295324 and PF-07259955) and vehicles (ointment and cream) will be supplied by Pfizer to the CRU as packaged 60 gram tubes and labeled according to local regulatory requirements in an unblinded fashion.

Both the IPs (PF-07295324 and PF-07259955) and vehicle doses will be prepared by the unblinded CRU pharmacist and provided to the blinded investigational site staff.

During the stay in the CRU, study drug applications will be performed by trained study staff to ensure proper study drug application.

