6.1.1. Administration

6.1.1.1. PF-07295324 and PF-07259955 Administration

The IP will be applied in blinded fashion, at the CRU. All applications of the IP will be dispensed and applied by study site staff from D1 AM through D10 AM dose. For Cohort 1 and Cohort 2, topical formulation will be applied Q12H on D1-D9 to the area identified on D-1 or D1. Only the AM dose will be applied on D10. Every effort must be made for the AM applications on D2 to D10 to be completed approximately 24±2 hour intervals from the recorded time of completion of the D1 dose application, for each participant. The PM dose application on D1 through D9 will be applied approximately 12±1 hour after the recorded time of completion of the AM dose application, for each participant.

For optional Cohort 3 and Cohort 4, formulation may be of a lower strength or equal to that of the planned cohort; administration procedures will be similar to that of planned cohorts. If study intervention in the optional cohort/s is once daily, formulation will be applied at AM only, from D1 to D10.

The per application dose will be calculated using the formula provided below in Section 6.1.1.2. The intended application rate is approximately 2.5 or 2 mg/cm^2 for PF-07295324 or PF-07259955, respectively. The IP should be applied evenly to all pre-specified areas. The per application dose will be expressed as the weight of ointment or cream in grams. The per application dose will remain fixed and the IP will be applied to the areas identified on Day 1.

In order to standardize the conditions on PK sampling days, all participants will be required to refrain from lying down for at least 4 hours post application (except when required for BP, pulse rate, and ECG measurements).

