6.1.1.2. Calculation of Per Application Dose

The per application dose (expressed in g) will be calculated by study site staff, for each participant, using the formula below:

BSA \times Application rate (g/cm²) = Weight of investigational product (in g) per application.

where BSA is less than or equal to 4000 cm^2 () and application rate is 2.5 mg/cm² (for cohorts assigned to PF-07295324/vehicle) and 2 mg/cm² (for cohorts assigned to PF-07259955/vehicle).

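### Protocol Section 6.7 defines overdose without a comparator and limits only strength, so an extra application or excess quantity does not clearly trigger its follow-up actions

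*Protocol*

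**What the plan says.** Section 6.7 opens by naming what counts as an overdose: "the maximum feasible formulation of IP specified below, Q12H to designated surface area within a 24-hour time period", with a 2-hour allowance. Two bullets follow. The first is "any dose of PF-07295324 greater than 0.12% within a 24-hour time period", and the second is the same for PF-07259955 at 2%.

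The section then lists the investigator's actions:

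- contact the medical monitor within 24 hours;
- monitor closely for adverse events and laboratory abnormalities for at least 5 half-lives or 28 calendar days, whichever is longer;
- "Document the quantity of the excess dose as well as the duration of the overdose in the CRF";
- draw a PK sample within 1 day of the last dose if the medical monitor asks for one.

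Elsewhere the protocol describes dose differently. Section 6.1 states that "the investigational products are PF-07295324 (0.12%), ointment and PF-07259955 (2%), cream", with matching vehicles. Section 4.3.2 says that strengths and dosing frequency in "optional Cohort 3 and/or Cohort 4 will not exceed that of Cohort 1 or Cohort 2". Section 6.1.1.1 says "The per application dose will be expressed as the weight of ointment or cream in grams", and Section 6.1.1.2 computes "Weight of investigational product (in g) per application" as treated area times application rate. Section 6.1.1.3 allows ±400 cm² around 4000 cm².

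**The concern.** The two halves of the definition fail in opposite directions. The lead-in has no comparator, so taken literally it covers every correctly dosed day in Cohorts 1 and 2. The bullets do have a comparator, but it applies to a quantity that can hardly be exceeded, because nothing stronger than 0.12% or 2% is supplied or allowed. The errors that could plausibly happen with a weighed topical product are an extra application, too much weight or too large an area. None of them changes the strength.

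The action list assumes a different definition. It asks for the size of the excess, but Section 6.7 gives no number of applications, weight or area from which to measure one.

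At stake is a directed follow-up in a first-in-human study. If site staff do not class the event as an overdose, the laboratory monitoring, the record of the excess quantity and duration, and the on-request PK sample are not clearly called for.

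**Working it through.** **Inputs.** Area up to 4000 cm² (Section 6.1.1.2). Rate 2.5 mg/cm² for PF-07295324 and 2 mg/cm² for PF-07259955 (Sections 6.1.1.1 and 6.1.1.2). Strengths 0.12% and 2% (Section 6.1). Two applications a day on Days 1 to 9 and one on Day 10 (Section 6.1.1.1).

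**Step 1: reproduce the planned daily dose.** Daily dose = area × rate × strength × applications per day.

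- PF-07295324: 4000 × 2.5 mg = 10 g per application; × 0.12% = 12 mg; × 2 = 24 mg/day. Table 3 gives 24 mg.
- PF-07259955: 4000 × 2 mg = 8 g per application; × 2% = 160 mg; × 2 = 320 mg/day. Table 4 gives 320 mg.

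**Step 2: add one application, or double the weight of one.**

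- PF-07295324: 3 × 12 = 36 mg/day.
- PF-07259955: 3 × 160 = 480 mg/day.
- Both are 36/24 = 480/320 = 1.5 times plan.

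**Step 3: compare with the tolerance already allowed.** At 4400 cm² and the same rate, the daily dose is 24 × 1.1 = 26.4 mg or 320 × 1.1 = 352 mg. The doses in Step 2 are well beyond that.

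**Step 4: test the Step 2 event against Section 6.7.**

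| Element | Limit as written | Third application | Met? |
|---|---|---|---|
| Lead-in | Planned regimen, no comparator | Planned regimen plus one | Unclear |
| Bullet 1 | Strength above 0.12% | 0.12% | No |
| Bullet 2 | Strength above 2% | 2% | No |

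Inserting *more than* in the lead-in would cover an extra application or excess area. It would still not clearly cover excess weight on the correct area at the correct frequency.

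**Step 5: what other sections require for the same event.**

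| Section 6.7 action | Other cover | Left open |
|---|---|---|
| Contact within 24 hours | Section 8.3.10: sponsor notice within 24 hours of a dosing error | Little |
| AE monitoring, at least 28 days | Section 8.3.1: AE collection to at least 28 days after the last dose | Little |
| Laboratory monitoring, at least 28 days | Scheduled labs end on Day 12; Day 41 is a phone contact; unscheduled labs are permitted (Sections 8.2, 8.2.4) | No other text directs it |
| Excess quantity and duration | Error recorded on the CRF (Section 8.3.10); doses weighed and times logged (Sections 6.2.1, 6.4) | Not asked for as such |
| PK sample on request | Scheduled on Days 1, 2, 5, 7 and 10 to 12; time points may be added (Section 8.4) | Days 3, 4, 6, 8 and 9 |

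Twenty-eight days after even a Day 1 event is Day 29, which is past discharge on Day 12.

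**Step 6: bound the exposure.** Unbound NOAEL average concentration ÷ projected unbound average concentration, using Tables 3 and 4:

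- PF-07295324: 88/0.48 = 183; at 1.5 times, 88/0.72 = 122.
- PF-07259955: 1691/16 = 106 (the table rounds to 110); at 1.5 times, 1691/24 = 70.
- PF-07259955 against the IFNγ IC50: 143/38.4 = 3.7; at 1.5 times, 143/57.6 = 2.5.

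These figures assume exposure proportional to dose and three applications every day. A single extra application adds one to a course of 9 × 2 + 1 = 19, or about 5% of the course dose. The 1.5-fold figures therefore overstate a one-day event.

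**The case against.** The best defence is that the meaning can be inferred. The lead-in mentions frequency and area, the bullets refer to a 24-hour period that would do no work if strength alone mattered, and the actions speak of an excess. Elsewhere the protocol uses the percentage as shorthand for the whole regimen, for example when Sections 2.2.2.1 and 2.2.2.2 project exposure from a twice-daily dose at the stated strength. Doses are weighed by pharmacy and applied by trained inpatient staff, so the error is unlikely. An extra application or excess weight would in any case fall under Section 8.3.10 as a medication error.

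Much of this stands. The intent is recoverable, and CRF recording, sponsor notice and AE collection do not depend on Section 6.7. It does not remove the point, because Section 8.3.10 directs neither the laboratory monitoring nor the PK sample, and does not ask for the excess quantity. A safety trigger should not have to be reconstructed from its neighbours.

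A reader might infer more than the documents support:

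- *Sites would treat correctly dosed participants as overdosed.* That follows only from the literal lead-in. The rest of the protocol makes the planned regimen plain.
- *An overdose would go unfollowed or a required blood draw would be missed.* Other sections keep AE collection and sponsor notice in place, and Section 6.7 fixes no laboratory visit or frequency.
- *One extra application would erode the safety margins.* Even the overstated calculation leaves NOAEL multiples of about 122 and 70.

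**Conclusion.** Wrong as written, and minor. The lead-in lacks its comparator, and the bullets limit only a quantity that no supplied product exceeds. A 50% excess in daily dose (36 mg against 24 mg, or 480 mg against 320 mg) therefore does not clearly trigger the Section 6.7 actions. What is lost is a clear instruction, chiefly for laboratory follow-up after Day 12 and for quantifying the excess.

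The daily doses rest on the full 4000 cm² and the stated application rates. The reassurance on margins rests on the protocol's own projections and on dose proportionality. No endpoint, analysis set, summary or stopping rule refers to the overdose definition, so the statistical results are unaffected.

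**What to change.** Reword Section 6.7 so that an overdose is more than the assigned dose in a dosing day, meaning any of:

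- more applications than assigned (2 for Q12H, 1 for once daily);
- application beyond the designated area, outside the existing ±400 cm² tolerance in Section 6.1.1.3;
- more than the participant's per-application weight calculated in Section 6.1.1.2;
- any strength above 0.12% (PF-07295324) or 2% (PF-07259955).

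The protocol gives a tolerance for area but none for weight, so any weight tolerance is for the sponsor to set. Add a cross-reference between Sections 6.7 and 8.3.10 so that a dosing error is checked against the overdose definition.

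The cost is new wording in one protocol section and one cross-reference. It needs no extra participants and no change to endpoints or analyses. Extra monitoring arises only if an overdose occurs.

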6.8. Concomitant Therapy

Use of prescription or nonprescription drugs and dietary and herbal supplements are prohibited within 7 days or 5 half-lives (whichever is longer) prior to the first dose of investigational product. Limited use of nonprescription medications that are not believed to affect participant safety or the overall results of the study may be permitted on a case-by-case basis following approval by the sponsor. Acetaminophen/paracetamol may be used at doses of $\leq 1 \text{ g/day}$.

All concomitant treatments taken during the study must be recorded with indication, daily dose, and start and stop dates of administration. All participants will be questioned about concomitant treatment at each clinic visit.

Treatments taken within 28 days before the first dose of investigational product will be documented as a prior treatment. Treatments taken after the first dose of investigational product will be documented as concomitant treatments.

6.8.1. Rescue Medicine

There is no rescue therapy to reverse the AEs observed with PF-07295324 and PF-07259955; standard medical supportive care must be provided to manage the AEs.

7. DISCONTINUATION OF STUDY INTERVENTION AND PARTICIPANT DISCONTINUATION/WITHDRAWAL

7.1. Discontinuation of Study Intervention

It may be necessary for a participant to permanently discontinue study intervention. Reasons for permanent discontinuation of study intervention include the following:

- Refused further follow-up;
- Lost to follow-up;
- Death;
- Study terminated by sponsor.

Note that discontinuation of study intervention does not represent withdrawal from the study. If study intervention is permanently discontinued, the participant will remain in the study to be evaluated for safety, tolerability, and skin irritation potential. See the SoA for data to be collected at the time of discontinuation of study intervention and follow-up for any further evaluations that need to be completed.

In the event of discontinuation of study intervention, it must be documented on the appropriate CRF/in the medical records whether the participant is discontinuing further receipt of study intervention or also from study procedures, posttreatment study follow-up, and/or future collection of additional information.

